2.3. Registry Rationale

Until recently, ICE has been limited to only two-dimensional (2D) imaging planes. Enabling real-time three-dimensional (3D) imaging with the Philips VeriSight combines the advantages of ICE with imaging capabilities that so far have only been available for TEE, and it has the potential to improve procedural guidance; quickly and easily locate guidewires, catheters, and devices; and provide greater anatomic information during percutaneous interventions. This novel real time 2D/3D ICE system has received US Food and Drug Administration clearance for commercial use and distribution. The purpose of this observational multi-center registry is to evaluate real-world safety and performance of VeriSight for ultrasound guided ICE imaging in percutaneous cardiac intervention procedures when used in standard clinical practice. The intended patient population are patients undergoing percutaneous cardiac intervention procedures for which VeriSight is indicated. The evidence from this post-market registry will be used for publications and to support regulatory filings outside of the US market.

2.4. Risk/Benefit Assessment

This will be an open-label all-comers registry. The design of the protocol is observational and there are no interventions as part of the registry. All interventions such as procedures occurring during this protocol are the standard clinical practice and their use will be directed by the investigator as part of the standard care. The Philips VeriSight ICE catheter has received 510(k) clearance from FDA allowing U.S. commercial sale. Investigators enrolling patients into the registry, will be imaged with the VeriSight catheter. Use of the product in this registry will be on label per the IFU and standard clinical practice. Patients will not be placed at additional clinical risk by participating in this registry. Although there are no added risks due to standard of care, the benefit at large will involve a better understanding of the safety profile for the ICE catheter tech within the respective intervention. Any complications associated with the VeriSight catheter and those related to the cardiac intervention procedures will be collected and reported.

3. REGISTRY DESIGN

3.1. General Description

This is a prospective, multi-center, observational, single-arm registry intended to gather real-world data to report VeriSight ICE catheter performance and safety. It will be conducted in the United States under the approval of one or more recognized institutional review boards and in compliance with GCP guidelines defined in ISO:14155:2011, the Declaration of Helsinki, and all applicable federal and local laws and regulations. Only on label uses of the VeriSight ICE catheter will be allowed. No specific claims are being validated during this registry, though data analyzed from this protocol are intended to inform of future claims regarding the performance and safety of the VeriSight catheter.

Document ID:	IGT_IGD_ICE Registry Study 2019 10745	Document title:		Classification:	Confidential
Modified:	24 APR 2021	Philips ICE Registry			
Version:	2.0	User Tool ID:	16.2.6UserTool0004		
Status:	Final	User Tool Version Date	30May2019	Page:	14

Clinical Registry Protocol
IGT_IGD_ICE Registry Study_2019_10745

Enrolled patients will be imaged with VeriSight for various types of percutaneous cardiac interventional procedures. Enrolled subjects will be followed until discharge or ≤48 hrs post-procedure. The registry has a planned duration of approximately 24-36 months with interim analysis planned at 100 patients before further enrollment will be considered. Statistical hypotheses are not intended for this registry and descriptive analysis will be conducted. Data from all clinical sites are intended to be pooled for analysis. It is possible that sub-analyses may be conducted to demonstrate VeriSight guidance for target intervention types in structural heart and electrophysiology procedures.

3.2. Performance and Safety Analyses

The overall purpose of this observational multi-center registry is to report real-world performance and safety of VeriSight ultrasound guided ICE imaging in percutaneous cardiac intervention procedures when used in standard clinical practice.

Primary Analyses

The primary analyses will include the following:

- a) **Technical success** – defined by successful delivery of VeriSight to the target intracardiac position and sustained device operation during the procedure
Successful device delivery is defined as ability of the VeriSight catheter to reach the target intracardiac anatomical position. Sustained operation of VeriSight is absence of technical complications or procedural delays/ disruption.
- b) **Imaging success** – Adequate image quality as determined by the investigator using a Likert scale assessment.
- c) **Clinical success** - Adequacy of VeriSight imaging for visualization of major cardiac structures, and guiding procedural intervention, and ability to detect/ assess intra-procedural complications.
Clinical success will be measured by ability of VeriSight to adequately guide procedural intervention using the following parameters:
 - i. number of great vessels imaged, number of chambers imaged, including angle of views, axis, and modality
 - ii. assessment of key cardiac structures and sizing relevant anatomy
 - iii. verification of delivery and/or placement of interventional device (e.g. trans septal puncture devices, closure devices (LAAO, PFO, ASD, VSD), valves (e.g for TAVR), clip devices (e.g. mitral clip), annuloplasty devices (e.g. Cardioband), ablation devices (e.g cryoballoon, RF ablation catheter), leads (leads extraction), etc.),
 - iv. assessment of procedural related complication (e.g. cardiac tamponade, pericardial effusion, thrombus) will be documented for each patient based on the procedure type.

Document ID:	IGT_IGD_ICE Registry Study_2019_10745	Document title:		Classification:	Confidential
Modified:	24 APR 2021	Philips ICE Registry			
Version:	2.0	User Tool ID:	16.2.6UserTool0004	Page:	15
Status:	Final	User Tool Version Date	30May2019		

Clinical Registry Protocol IGT_IGD_ICE Registry Study_2019_10745

d) **Safety** - Device related adverse events periprocedural through discharge or 48 hours post-procedure, whichever is earlier.

Secondary Analyses

Secondary analyses will include the following:

- a) Procedural characterization when using VeriSight measured by
 - i. type of procedure utilizing ICE imaging
 - ii. total procedural room time (door-in to door-out, mins), total procedure time (skin to skin, mins)
 - iii. total fluoroscopy time (mins)
 - iv. total contrast volume used (cc), fluoroscopic dosage (mGy)
 - v. ability to image from the right side of the heart for a left sided intervention
 - vi. TEE usage rate and avoidance of TEE procedure
 - vii. Other imaging modality used during the procedure
 - viii. Change in management from use of VeriSight – need for high risk patient and/or procedure management
 - ix. Duration and type of anesthesia
 - x. Freedom from general anesthesia
- b) Device characterization when using VeriSight based on a scoring scale for the physical attributes of the VeriSight catheter
- c) Physician survey regarding the Philips ICE using a five-point ordinal Likert-type rating scale
- d) Staff survey regarding the Philips ICE using a five-point ordinal Likert-type rating scale

3.3. Measures to Minimize Bias

The following measures will be taken to minimize and/or avoid bias in this registry:

- a) A multi-center observational registry design is used to help ensure a representative sample of physicians performing the procedure and to provide a reasonable enrollment period.
- b) Sites will have the ability to represent all-comers in various percutaneous cardiac intervention procedures.
- c) Subjects will be screened to confirm study eligibility with defined inclusion/exclusion criteria prior to inclusion. Sites are required to maintain a log of all subjects screened and enrolled for the study.
- d) Data collection requirements and study procedures will be standardized across all sites. All sites will follow the same version of the protocol and eCRFs.
- e) Collection and archiving of image data will be managed adequately to reduce the impact of data loss and error in analysis.

Document ID:	IGT_IGD_ICE Registry Study_2019_10745	Document title:		Classification:	Confidential
Modified:	24 APR 2021	Philips ICE Registry			
Version:	2.0	User Tool ID:	16.2.6UserTool0004		
Status:	Final	User Tool Version Date	30May2019	Page:	16

Clinical Registry Protocol
IGT_IGD_ICE Registry Study_2019_10745

- f) Standardized protocol training will be developed and distributed to all participating sites to ensure data of uniform quality are obtained from all subjects
- g) Regular monitoring will be conducted to verify source data and adherence to the protocol.

4. REGISTRY POPULATION

4.1. Inclusion Criteria

1. 18 years of age and willing to provide written, dated and signed, informed consent
2. Scheduled for a procedure that is within the scope of clinical indication for VeriSight per Instructions for Use (IFU)

4.2. Exclusion Criteria

Patients who have ANY of the following exclusion criteria are NOT eligible for participation on the registry.

1. Contraindicated for ICE catheter placement or patient considerations that make placement of VeriSight not technically feasible
2. If alternate access (as needed instead of femoral) is not viable
3. Known contraindicated conditions include sepsis, major coagulation abnormalities, presence of any intracardiac thrombus, presence of class IV angina or heart failure, deep vein thrombosis, or significant peripheral vascular disease.

4.3. Number of Subjects

Enrollment of up to 200 all-comers is planned with distribution across multiple case types such as structural heart disease interventions and electrophysiology procedures. Based on a sample of 100 patients, minimum representation of anticipated enrollment for each procedure type based on investigator survey is the following: minimum of 30 cases for electrophysiology, minimum of 30 cases for left atrial appendage occlusion, minimum of 20 cases for valve intervention, and 5 for ASD/PFO. Each participating registry site will be allowed a maximum enrollment of no more than 30% patients from the total planned enrollment.

4.4. Enrollment

Subjects who sign the informed consent form and are indicated for treatment procedure per VeriSight commercial labeling will be considered for the registry. A subject is considered enrolled in the registry when VeriSight has been placed in their vasculature and the device is switched “ON”. Participation is complete at discharge or ≤48 hours post-procedure from the registry site, whichever occurs first.

Document ID:	IGT_IGD_ICE Registry Study 2019 10745	Document title:		Classification:	Confidential
Modified:	24 APR 2021	Philips ICE Registry			
Version:	2.0	User Tool ID:	16.2.6UserTool0004	Page:	17
Status:	Final	User Tool Version Date	30May2019		

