4.5. Screen Failures

Only consented subjects who are considered enrolled in the registry will be followed. Those who provide consent, but then are determined to be ineligible at the time of enrollment will be considered screen failures.

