8.2. Populations for Analyses

All subjects age 18 and older that are scheduled for and will undergo a planned cardiac interventional percutaneous procedure in which the guidance of ICE is indicated, eligible and willing to sign an informed consent without meeting any of the exclusion criteria set and meeting all the inclusion criteria set forth in the protocol will be included in the population for analyses. Those who sign consent but do not undergo a cardiac procedure utilizing the Philips ICE catheter will be excluded from the analyses (screen failures).

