8.3. Statistical Analyses

No formal statistical hypothesis test is planned and the primary and secondary endpoints will be presented as descriptive statistics only. An interim analysis will be conducted following 100th patient enrollment to monitor, measure, and review performance and safety measures prior to determination of further enrollment in the registry.

Document ID:	IGT_IGD_ICE Registry Study 2019 10745	Document title:		Classification:	Confidential
Modified:	24 APR 2021	Philips ICE Registry			
Version:	2.0	User Tool ID:	16.2.6UserTool0004	Page:	27
Status:	Final	User Tool Version Date	30May2019		

Clinical Registry Protocol
IGT_IGD_ICE Registry Study_2019_10745

Statistical analyses will be done on the real-world, all-comer population and presented as descriptive statistics and 95% confidence intervals. Subject data from all clinical sites are intended to be pooled for analysis to broaden demographic representation. However, it is possible that sub-analyses may be conducted in a population stratified by procedure characteristics and baseline characteristics.

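### Because enrolment starts only once VeriSight is in the vasculature and ON, a permanent failure to insert or start it can drop out of the technical-success denominator

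*Protocol*

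**What the plan says.** **The endpoint.** Protocol 3.2 and SAP 5.3.1 define technical success as "successful delivery of VeriSight to the target intracardiac position and sustained device operation during the procedure". SAP 8.7.1 reports it as a proportion with an exact two-sided 95% interval but names no denominator. SAP 8.2.1 says that neither an intent-to-treat nor a per-protocol population will be used.

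**Entry.** Protocol 4.4: "A subject is considered enrolled in the registry when VeriSight has been placed in their vasculature and the device is switched" on. Protocol 4.5: "Only consented subjects who are considered enrolled in the registry will be followed". The Protocol Summary promises that enrolled subjects will be accounted for in the report; it makes no such promise for anyone else.

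**Exclusion from analysis.** Protocol 8.2, repeated in SAP 4.3: "Those who sign consent but do not undergo a cardiac procedure utilizing the Philips ICE catheter will be excluded from the analyses (screen failures". The word *utilizing* is not defined.

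**Text pointing the other way.** The first sentence of Protocol 8.2 takes in eligible, consenting adults "scheduled for and will undergo a planned cardiac interventional percutaneous procedure in which the guidance of ICE is indicated", with no condition that the catheter was placed. Protocol 4.5 confines screen failure to ineligibility: "Those who provide consent, but then are determined to be ineligible at the time of enrollment will be considered screen failures". Protocol 8.3: "Statistical analyses will be done on the real-world, all-comer population".

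**The concern.** Entry to the registry depends on part of the outcome being measured. A catheter that cannot be inserted, or that never starts, has been neither delivered nor kept in operation. Under Protocol 4.4 that patient is not enrolled, and under the second sentence of Protocol 8.2 the patient can be called a screen failure. A technical failure then becomes a patient who was never in the analysis.

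The registry is descriptive, so the estimate and its interval are the product. SAP 4.1 intends the analysis at 100 subjects for a CE mark submission. No hypothesis or performance goal is stated, so what is at stake is the accuracy of the reported rate, not a pass or fail decision. Sites keep a log of subjects screened and enrolled (Protocol 3.3), and malfunctions follow commercial procedures (Protocol 7.2), but nothing commits the report to showing how many attempts failed before enrolment.

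**Working it through.** **Step 1: which patients are affected.** Take a consented patient judged eligible at screening.

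- *Catheter in the vasculature and ON, then fails to reach the target or stops working:* enrolled, counted as a failure. No gap.
- *First attempt fails, a retry or replacement succeeds:* enrolled. Protocol 6.4 records the number of attempts, malfunctions and delays. No gap.
- *Device never starts, and the procedure goes ahead under other imaging:* not enrolled under 4.4. Excluded if *utilizing* means imaging was obtained; included on the first sentence of 8.2; not a screen failure under 4.5, because the patient is not ineligible.
- *Catheter can never be inserted, for reasons of anatomy or access:* as above, with a second route out. Exclusion 1 in Protocol 4.2 covers "patient considerations that make placement of VeriSight not technically feasible", and 4.5 judges ineligibility at enrolment, which under 4.4 comes after placement. This route rests on patient considerations and does not reach a device start-up fault.

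Only the last two cases are open.

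**Step 2: direction.** Let n be the number enrolled, s the successes among them, and k the permanent failures before enrolment. The rate without them is s/n; with them it is s/(n + k). The difference is

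s/n − s/(n + k) = s·k / [n(n + k)],

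which is positive whenever s and k are at least 1 and zero when s = 0. Omission can never lower the rate.

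**Step 3: size.** The plan states no rate or precision target behind its sample size, so there is no figure of its own to reproduce. Inputs from the documents: n = 100 (interim) and n = 200 (maximum), with the SAP's Clopper-Pearson method. Assumptions: k = 1 or 3, and 100% or 95% success among enrolled patients. The lower limit is the 0.025 quantile of Beta(s, N − s + 1) and the upper limit the 0.975 quantile of Beta(s + 1, N − s), where N = n + k; the upper limit is 100% when s = N.

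| Enrolled, successes | k = 0 | k = 1 | k = 3 |
|---|---|---|---|
| 100, 100 | 100.0% (96.4–100) | 100/101 = 99.0% (94.6–99.97) | 100/103 = 97.1% (91.7–99.4) |
| 100, 95 | 95.0% (88.7–98.4) | 95/101 = 94.1% (87.5–97.8) | 95/103 = 92.2% (85.3–96.6) |
| 200, 200 | 100.0% (98.2–100) | 200/201 = 99.5% (97.3–99.99) | 200/203 = 98.5% (95.7–99.7) |
| 200, 190 | 95.0% (91.0–97.6) | 190/201 = 94.5% (90.4–97.2) | 190/203 = 93.6% (89.3–96.5) |

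Per omitted patient (k = 1), the overstatement is 0.99 or 0.94 points at n = 100, and 0.50 or 0.47 points at n = 200.

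**The case against.** Enrolling at first device use is a defensible choice for an on-label, descriptive imaging registry, and SAP 4.1 says that no specific claims are being validated. Protocol 6.1 and 6.3 also use enrolment language more loosely, placing enrolment activities at the screening visit. Permanent failure before ON, with no successful retry, may be rare or absent. All of this stands, and it limits the weight of the point. It does not settle the denominator: 4.4 is the explicit definition, and the conflict between the two sentences of 8.2 remains.

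Three stronger readings are tempting and are not supported.

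- *That any failed case can be relabelled ineligible.* Exclusion 1 concerns the patient, not the device. Protocol 6.3 and Table 1 place the eligibility assessment at screening, and Protocol 3.3 requires it before inclusion. What remains is the loose timing phrase in 4.5, and only for patient-related placement failure. Such a patient may in truth lie outside the intended population, which is why the reason for each failure should be reported.
- *That the published rate will be inflated.* The direction is certain if such a patient occurs and is left out. The documents give no frequency.
- *That an injury during a failed insertion would go unreported.* Protocol 7.7 starts collection of adverse device effects at enrolment, and one sentence of 7.3 limits reporting to events under VeriSight guidance. But 7.3 also requires all adverse device effects to be reported to the sponsor, 7.2 puts malfunction-related harm on the case report form, and 2.4 promises collection of catheter-associated complications. The passages disagree; a loss of events is not shown.

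**Conclusion.** The point holds as an unresolved conflict over the denominator of a primary analysis. The main route is Protocol 4.4 together with the undefined *utilizing* in Protocol 8.2 and SAP 4.3; exclusion 1 read with 4.5 is a secondary route for patient-related placement failure only. The error is one-sided, about 1 point per omitted patient at 100 enrolled and about 0.5 at 200, and zero if no such patient occurs. This rests on counting a permanent failure to place or start as a technical failure, which is the plain meaning of Protocol 3.2, and on assumed counts. It is worth fixing because the remedy is cheap and the interim figures are meant for a regulator.

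**What to change.** In Protocol 4.4, 4.5 and 8.2 and SAP 4.3:

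1. Make the technical-success denominator all consented patients judged eligible at screening in whom VeriSight use was attempted, with *attempted* defined. Count permanent failure to place or start as technical failure.
2. Define *utilizing* and screen failure to match, and replace the timing phrase in 4.5 with eligibility settled before the attempt.
3. Report the number attempted but not enrolled, with the reason (device or patient), and give enrolled-set results alongside.

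For safety, only reconcile the start of collection in Protocol 7.7 and the guidance-limited sentence in 7.3 with 2.4, 7.2 and the other reporting sentence in 7.3.

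Cost: a short amendment needing IRB approval, matching SAP wording, and a small eCRF field, because Protocol 6.4 records attempts only for enrolled subjects. The screening log can help identify the others. The reported rate may be slightly lower.

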4.5. Screen Failures

Only consented subjects who are considered enrolled in the registry will be followed. Those who provide consent, but then are determined to be ineligible at the time of enrollment will be considered screen failures.

4.6. Registry Exit Definition

A subject is considered to have completed and exited the registry if he or she has completed all phases of the study including the last visit or the last scheduled procedure shown in the **Schedule of Activities (SoA), Section 6.2**.

4.7. Subject Discontinuation/Withdrawal from the Study

Study participation is voluntary. The subject may refuse to consent or may withdraw from the study at any time without penalty or loss of benefits of quality of care to which he/she is otherwise entitled. All information regarding the subject's withdrawal must be recorded in the subject's medical record. In addition, the appropriate case report forms must be completed for the Subject and clear documentation of the subject's withdrawal must be provided to the Sponsor.

4.8. Lost to Follow-Up

Follow-up in this registry is limited to discharge or ≤48 hours post-procedure, whichever is earlier. All follow-up data is expected to be collected and lost to follow-up is not anticipated in this registry.

4.9. Registry Duration

The expected duration of the registry is estimated to be approximately 24 – 36 months.

5. DEVICE ACCOUNTABILITY

The Philips VeriSight catheter is a commercially approved device that will be used within their approved indication. The intended indication is for intracardiac and intra-luminal visualization of cardiac and great vessel anatomy and physiology as well as visualization of other devices in the heart. A complete description of the VeriSight catheter can be found in the product's IFU.

The Philips VeriSight catheter will be purchased by each site and will not require product packing and shipment information to be tracked. The EPIC console will be loaned to site with the latest software for use with the VeriSight ICE catheter.

Document ID:	IGT_IGD_ICE Registry Study 2019_10745	Document title:		Classification:	Confidential
Modified:	24 APR 2021	Philips ICE Registry			
Version:	2.0	User Tool ID:	16.2.6UserTool0004	Page:	18
Status:	Final	User Tool Version Date	30May2019		

6. REGISTRY PROCEDURES & EVALUATIONS

Subjects enrolled in this registry will have at least one visit and may have up to three visits, depending on the scheduling of their procedure at each clinical site. Individual visits and their specific procedures will consist of the events described below.

